### 17.2.1.1 PRESENTATION OF 30-MINUTE SOLICITED LOCAL AND SYSTEMIC REACTOGENICITY

The following will be presented for the FA population:

1. Subject-wise listing of 30-minute solicited local and systemic reactogenicity will be generated separately.
2. Summary of 30-minute solicited local and systemic reactogenicity will be provided separately as follows:
  - 
  - Count and percentages of participants experiencing each reaction or event, or at least one reaction or event will be calculated along with two-sided exact 95% CIs using Clopper-Pearson method (refer [Appendix 2](#)) for each treatment group, and by age group.
  - Fisher's exact test (refer [Appendix 3](#)) or Cochran-Mantel-Haenszel test (refer [Appendix 4](#)) will be used to compare the proportion of participants between the two treatment groups.
3. Descriptive summary (as described for continuous variables in [Section 6](#)) of the size of the solicited local reactions captured in 30-minute reactogenicity page of the eCRF will be presented by vaccine and placebo.
4. In addition, for all Solicited Local and Systemic Adverse Events, the following will be summarised by severity:
  - Counts of all events will be reported and summarized, as "any local AE" or "any systemic AE".

---

Document:	\\EEDC-NAS01A\Biosdata\Path\IVACFLU-S\IYA06804\Biostatistics		
	Documentation\SAP\IVACFLU-S-0203_SAP_Draft v1.0		
Author:	[name]	Version Number:	1.0
		Version Date:	[11AUG2017]
Template No:	CS_TP_BS016 Revision 4	Reference:	CS_WI_BS005
Effective Date:	01Apr2016		

- Percentages of subjects experiencing each reaction or event, at least one reaction or event will be calculated. This will be generated separately i.e., one output for Body temperature (Oral) and one output for all other adverse events, as the severity grades will be as follows:
  - Body temperature (Oral):
    - Ungradable
    - Grade 1= '38.0 - <38.6°C'
    - Grade 2= '38.6 – <39.3°C'
    - Grade 3=' 39.3 – <40.0°C'
    - Grade 4=' ≥ 40.0°C'
  - For local and systemic adverse events:
    - None
    - Mild
    - Moderate
    - Severe
    - Potentially Life Threatening

### 17.2.1.2 PRESENTATION OF SOLICITED LOCAL AND SYSTEMIC ADVERSE EVENTS

The following will be presented for the FA population:

1. Subject-wise listing of solicited local and systemic adverse events will be generated separately.
2. Summary of solicited local and systemic adverse events will be provided separately as follows:
  - Counts and percentages of subjects experiencing each reaction or event, at least one reaction or event will be calculated.
  - Number of events for each reaction or event will also be displayed.
  - Event will be counted only one time if occurred on consecutive days.

Percentages of participants experiencing each reaction or event, or at least one reaction or event will be calculated along with two-sided exact 95% CIs using Clopper-Pearson method (refer [Appendix 2](#)) for each treatment group and by age group. Fisher's exact test (refer [Appendix 3](#)) or Cochran-Mantel-Haenszel test (refer [Appendix 4](#)) will be used to compare the proportion of participants between the two treatment groups.

3. Summary of solicited local and systemic adverse events, as described in the above point 2 will be repeated i.e., summarized by day:

---

Document:	\\EEDC-NAS01A\Biosdata\Path\IVACFLU-S\IYA06804\Biostatistics		
	Documentation\SAP\IVACFLU-S-0203_SAP_Draft v1.0		
Author:	[name]	Version Number:	1.0
		Version Date:	[11AUG2017]
Template No:	CS_TP_BS016 Revision 4	Reference:	CS_WI_BS005
Effective Date:	01Apr2016		

- Counts and percentages of subjects experiencing each reaction or event, at least one reaction or event will be calculated.
  - Number of events for each reaction or event will also be displayed.
4. Descriptive summary (as described for continuous variables in [Section 6](#)) of the size of the solicited local reactions captured as per the eCRF will be presented by vaccine and placebo.

In addition, for all Solicited Local and Systemic Adverse Events the following will be summarised by maximum severity until resolution:

- Counts of all events will be reported and summarized, as “any local AE” or “any systemic AE”.
- Percentages of subjects experiencing each reaction or event, at least one reaction or event will be calculated. This will be generated separately i.e., one output for Body temperature (Oral) and one output for all other adverse events, as the severity grades will be as follows:
  - Body temperature (Oral):
    - Ungradable
    - Grade 1= ‘38.0 - <38.6°C’
    - Grade 2= ‘38.6 – <39.3°C’
    - Grade 3= ‘39.3 – <40.0°C’
    - Grade 4= ‘≥ 40.0°C’
  - For local and systemic adverse events:
    - None
    - Mild
    - Moderate
    - Severe
    - Potentially Life Threatening

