## 17. SAFETY OUTCOMES

### 17.1 STATISTICAL CONSIDERATIONS:

Null hypothesis ( $H_0$ ):

A single dose of seasonal trivalent inactivated split virion influenza vaccine (IVACFLU-S) is not safe and well tolerated in adults 18 to 60 years of age.

Alternative hypothesis ( $H_1$ ):

A single dose of seasonal trivalent inactivated split virion influenza vaccine (IVACFLU-S) is safe and well tolerated in adults 18 to 60 years of age.

The total sample size for Phase 2 and Phase 3 combined will be 888 subjects. With subjects randomized to IVACFLU-S or placebo at a randomization ratio of 5:1, there will be 740 subjects randomized to IVACFLU-S arm in the phase 2/3 study. Accounting for a 5% dropout rate, there would be at least 700 evaluable participants for safety analysis. If no vaccine-related serious adverse events are observed in 700 vaccine recipients, the study would be able to exclude events occurring at approximately 0.43% based on the upper bound of the one sided 95% Confidence Interval (CI) using the Clopper-Pearson method.

The probability of observing at least one vaccine-related serious adverse event in 700 subjects is 90 % and >95% if the true rate of such events is 0.33 % and 0.43% respectively. The precision of the estimate of AEs judged to be related to IVACFLU-S as bounded by 95% CI is presented in Table 7.

Table 7: Exact 95% Confidence Intervals around Potential Number of Study Related Adverse Events

Sample size	Number of events	2-sided exact 95% CI
700	0	[0, 0.52*]
	1	[<0.01, 0.79]
	2	[0.03, 1.02]
	3	[0.08, 1.24]
	5	[0.23, 1.65]

\*one sided, 97.5% CI

Document: \\EEDC-NAS01A\Biosdata\Path\IVACFLU-S\IYA06804\Biostatistics  
Documentation\SAP\IVACFLU-S-0203\_SAP\_Draft v1.0

Author: [name]

Version Number:

1.0

Version Date:

[11AUG2017]

Template No: CS\_TP\_BS016 Revision 4  
Effective Date: 01Apr2016

Reference: CS\_WI\_BS005

However, the full analysis population will be used for safety analysis, not the assumed number of 700 evaluable subjects.

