SAEs: At Any Time	xx	(xx.x)	[xx.xx, xx.xx]	xx	xx	(xx.x)	[xx.xx, xx.xx]	xx		xx	(xx.x)	[xx.xx, xx.xx]	xx
Severe	xx	(xx.x)	[xx.xx, xx.xx]	xx	xx	(xx.x)	[xx.xx, xx.xx]	xx		xx	(xx.x)	[xx.xx, xx.xx]	xx
Related	xx	(xx.x)	[xx.xx, xx.xx]	xx	xx	(xx.x)	[xx.xx, xx.xx]	xx		xx	(xx.x)	[xx.xx, xx.xx]	xx
Deaths	xx	(xx.x)	[xx.xx, xx.xx]	xx	xx	(xx.x)	[xx.xx, xx.xx]	xx		xx	(xx.x)	[xx.xx, xx.xx]	xx
Any AE leading to study withdrawal	xx	(xx.x)	[xx.xx, xx.xx]	xx	xx	(xx.x)	[xx.xx, xx.xx]	xx		xx	(xx.x)	[xx.xx, xx.xx]	xx

Document: \\EEDC-NAS01A\Biosdata\Path\IVACFLU-S\IYA06804\Biostatistics \Documentation\SAP\IVACFLU-S-0203\_Mock\_Tables\_V1.0  
 Author: [name]  
 Version Number: 1.0  
 Version Date: 11AUG 2017

Template No: CS\_TP\_BS016 Revision 4  
 Effective Date: 01Apr2016  
 Reference: CS\_WI\_BS005

---

 TABLE AND LISTING MOCK SHELL
 

---

Data is based on the combined phases 2 and 3, pooled across study sites.

AE: Adverse Events, SAE: Serious Adverse Events

N= Total number of subjects in the relevant population per by-group stratification level, n= Number of subjects in each category, E= Number of Adverse Events, % = Calculated relative to the total number of subjects in the relevant population

Any solicited local or systemic reactogenicity that occurs during the 5-day period post-injection is automatically regarded as related.

Solicited AEs captured within 30 minutes and between day 1 to day 7 after administration of treatment were considered.

\*95% confidence interval (CI) for single proportion: Calculated using Clopper-Pearson method for a single binomial proportion.

p-value: Calculated using Fisher's exact test

Source Data: Listing 16.2.7.1, 16.2.7.2, 16.2.7.4, 16.2.7.5

Programming Note: Please note that p-value calculated using Fisher's exact test should be displayed for solicited AEs only.

---

Document: \\EEDC-NAS01A\Biosdata\Path\IVACFLU-S\IYA06804\Biostatistics \Documentation\SAP\IVACFLU-S-0203\_Mock\_Tables\_V1.0

Author: [name]

Version Number:

1.0

Version Date:

11AUG 2017]

Template No: CS\_TP\_BS016 Revision 4

Reference: CS\_WI\_BS005

Effective Date: 01Apr2016

Copyright © 2009, 2010, 2012, 2016 Quintiles Transnational Corp. All rights reserved.

The contents of this document are confidential and proprietary to Quintiles Transnational Corp. Unauthorized use, disclosure or reproduction is strictly prohibited.

TABLE AND LISTING MOCK SHELL

Table 14.3.2.1.1  

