Incidence of Solicited Local Adverse Events from Day 1 to Day 7  
Full Analysis Population

Age Group: <Overall> <18-45> <46-60>

	Vaccine (N=XX)				Placebo (N=XX)				P-value	Total (N=XX)				
	n	(%)	[95% CI]*	E	n	(%)	[95% CI]*	E		n	(%)	[95% CI]*	E	
...														
Solicited Local Adverse Events	xx	(xx.x)	[xx.xx, xx.xx]	xx	xx	(xx.x)	[xx.xx, xx.xx]	xx	0.xxxx		Xx	(xx.x)	[xx.xx, xx.xx]	xx
Subjects with at least one solicited Local AE	xx	(xx.x)	[xx.xx, xx.xx]	xx	xx	(xx.x)	[xx.xx, xx.xx]	xx	0.xxxx		xx	(xx.x)	[xx.xx, xx.xx]	xx
Redness	xx	(xx.x)	[xx.xx, xx.xx]	xx	xx	(xx.x)	[xx.xx, xx.xx]	xx	0.xxxx		xx	(xx.x)	[xx.xx, xx.xx]	xx
Swelling	xx	(xx.x)	[xx.xx, xx.xx]	xx	xx	(xx.x)	[xx.xx, xx.xx]	xx	0.xxxx		xx	(xx.x)	[xx.xx, xx.xx]	xx
...	xx	(xx.x)	[xx.xx, xx.xx]	xx	xx	(xx.x)	[xx.xx, xx.xx]	xx	0.xxxx		xx	(xx.x)	[xx.xx, xx.xx]	xx
...														

Data is based on the combined phases 2 and 3, pooled across study sites.  
 N= Total number of subjects in the relevant population per by-group stratification level, n= Number of subjects in each category, E= Number of Adverse Events, % = Calculated relative to the total number of subjects in the relevant population  
 \*95% confidence interval (CI) for single proportion: Calculated using Clopper-Pearson method for a single binomial proportion.  
 P-value: Calculated using Fisher's exact test or Cochran-Mantel-Haenszel test comparing vaccine groups.  
 Event will be counted only one time if occurred on consecutive days.  
 Source Data: Listing 16.2.7.1

Table 14.3.2.1.2

Document:	\\EEDC-NAS01A\Biosdata\Path\IVACFLU-S\IYA06804\Biostatistics \Documentation\SAP\IVACFLU-S-0203_Mock_Tables_V1.0	Version Number:	1.0
Author:	[name]	Version Date:	11AUG 2017
Template No:	CS_TP_BS016 Revision 4	Reference:	CS_WI_BS005
Effective Date:	01Apr2016		

TABLE AND LISTING MOCK SHELL

---

Incidence of Solicited Systemic Adverse Events from Day 1 to Day 7  
Full Analysis Population

Source Data: Listing 16.2.7.2.  
Programming Note: Repeat the template of Table 14.3.2.1.1 with appropriate changes.

---

Document:	\\EEDC-NAS01A\Biosdata\Path\IVACFLU-S\IYA06804\Biostatistics \Documentation\SAP\IVACFLU-S-0203_Mock_Tables_V1.0		
Author:	[name]	Version Number:	1.0
		Version Date:	11AUG 2017]
Template No:	CS_TP_BS016 Revision 4	Reference:	CS_WI_BS005
Effective Date:	01Apr2016		

TABLE AND LISTING MOCK SHELL

Table 14.3.2.1.3  
Incidence of Solicited 30 minutes Local Adverse Event  
Full Analysis Population

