Days: Derived relative to administration date/time of vaccination.

Document: \\EEDC-NAS01A\Biosdata\Path\IVACFLU-S\IYA06804\Biostatistics \Documentation\SAP\IVACFLU-S-0203\_Mock\_Tables\_V1.0  
 Author: [name]  
 Version Number:  
 Version Date:

1.0  
11AUG 2017]

Template No: CS\_TP\_BS016 Revision 4  
Effective Date: 01Apr2016

Reference: CS\_WI\_BS005

Copyright © 2009, 2010, 2012, 2016 Quintiles Transnational Corp. All rights reserved.  
The contents of this document are confidential and proprietary to Quintiles Transnational Corp. Unauthorized use, disclosure or reproduction is strictly prohibited.

TABLE AND LISTING MOCK SHELL

Table 14.3.6.1  
Summary of Vital Signs  
Full Analysis Population

Age Group: <Overall> <18-45> <46-60>											
Assessment (Unit)	Visit	Outcome	Statistic	Vaccine (N=xx)		Placebo (N=xx)		Total (N=xx)		p-value ^	
				Actual	CFB	Actual	CFB	Actual	CFB		
Body Temperature(°C)	Screening	Result	n	xx		xx		xx			
			Mean	xx.x		xx.x		xx.x			
			Median	xx.x		xx.x		xx.x			
			SD	xx.xx		xx.xx		xx.xx			
			Min, Max	xx, xx		xx, xx		xx, xx			
			Missing	xx		xx		xx			
	Day 8	Result	n	xx	xx	xx	xx	xx	xx	xx	0.xxxxxx
			Mean	xx.x	xx.x	xx.x	xx.x	xx.x	xx.x	xx.x	
			Median	xx.x	xx.x	xx.x	xx.x	xx.x	xx.x	xx.x	
			SD	xx.xx	xx.xx	xx.xx	xx.xx	xx.xx	xx.xx	xx.xx	
			Min, Max	xx, xx	xx, xx	xx, xx	xx, xx	xx, xx	xx, xx	xx, xx	
			missing	xx	xx	xx	xx	xx	xx	xx	
			p-value*	0.xxxxxx		0.xxxxxx					

Data is based on the combined phases 2 and 3, pooled across study sites.  
 CFB: Change From Baseline; Max: Maximum; Min; Minimum; SD: Standard Deviation  
 N= Total number of subjects in relevant population per by-group stratification level. n= Number of subjects with an assessment.  
^P-value was computed using or 2-sample t test comparing vaccine groups.  
 \* P-value was computed using paired t test comparing vaccine groups.  
 Source Data: Listing 16.2.8.2

Programming Note: Summarize for the parameters systolic blood pressure (mmHg), diastolic blood pressure (mmHg) and pulse rate (beats/min).

Document: \\EEDC-NAS01A\Biosdata\Path\IVACFLU-S\IYA06804\Biostatistics \Documentation\SAP\IVACFLU-S-0203\_Mock\_Tables\_V1.0  
 Author: [name]  
 Version Number: 1.0  
 Version Date: 11AUG 2017  
 Template No: CS\_TP\_BS016 Revision 4  
 Effective Date: 01Apr2016  
 Reference: CS\_WI\_BS005

Copyright © 2009, 2010, 2012, 2016 Quintiles Transnational Corp. All rights reserved.  

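### SAP 17.1 states a safety null and alternative that no planned analysis tests; give the vaccine-minus-placebo difference in solicited adverse events with a 95% CI and restate safety as estimation

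*Combined protocol and SAP*

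**What the plan says.** SAP 17.1 writes safety as a pair of hypotheses: under the null the vaccine "is not safe and well tolerated in adults 18 to 60 years of age", and under the alternative it is. Neither carries a rate, a difference or a margin. The precision figures in the same section (about 0.43% excluded if no events occur in 700, and Table 7) concern the vaccine arm alone.

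For solicited events, SAP 17.2.1.1 (30 minutes) and 17.2.1.2 (Days 1 to 7) plan percentages with "two-sided exact 95% CIs using Clopper-Pearson method" for each arm and age group. They add that Fisher's exact or the Cochran-Mantel-Haenszel test "will be used to compare the proportion of participants between the two treatment groups". The protocol synopsis sets the level at two-sided 0.05.

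The shells follow this. Tables 14.3.2.1.1 to 14.3.2.1.4 show n, %, a per-arm CI, an event count and a p-value from Fisher's "exact test or Cochran-Mantel-Haenszel test comparing vaccine groups". In Table 14.3.1.1 the interval is "Calculated using Clopper-Pearson method for a single binomial proportion", and the programming note says Fisher p-values "should be displayed for solicited AEs only". No risk difference, ratio or CI for a between-arm contrast appears in the protocol, SAP or shells.

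Protocol 13.7 evaluates safety by numbers and proportions, and says that no formal, multiplicity-adjusted hypothesis testing will be done. SAP 3.3 records no change from the protocol.

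**The concern.** The stated hypotheses and the planned test ask different questions. Fisher and Cochran-Mantel-Haenszel both take no difference between arms as the null. Failing to reject that is not evidence of safety, and rejecting it with more events on vaccine is evidence of more reactions. The pair in 17.1 is therefore left untested whichever way the data fall.

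The practical risk lies in interpretation. Solicited events are primary safety endpoints, and the placebo arm is there to put them in context. A p-value well above 0.05, with no interval for the difference beside it, is easily taken to mean that the vaccine is no different from placebo, when an excess of several points may still fit the data. Many unadjusted p-values also leave room for chance signals.

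**Working it through.** **1. The plan's own figures.** With 0 events in 700, the one-sided 95% upper limit is 1 - 0.05^(1/700) = 0.427%, which matches 0.43%. The chance of at least one event is 1 - (1 - 0.0033)^700 = 90.1% and 1 - (1 - 0.0043)^700 = 95.1%, as stated. These figures are sound, but they say nothing about vaccine against placebo.

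**2. Arm sizes.** At 5:1, 888 × 5/6 = 740 vaccine and 888/6 = 148 placebo. Per age group (protocol Table 15): 105 + 265 = 370 and 21 + 53 = 74. All randomised participants are assumed to be vaccinated and to contribute data.

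**3. An assumed modest excess, 15% vaccine against 10% placebo.** Approximate (Wald) 95% half-width of the difference, 1.96 × √(p1q1/n1 + p0q0/n0):
- overall: 1.96 × √(0.1275/740 + 0.09/148) = 1.96 × √(0.000172 + 0.000608) = 5.5 points
- per age group: 1.96 × √(0.1275/370 + 0.09/74) = 1.96 × √(0.000345 + 0.001216) = 7.7 points

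Two-sided Fisher power at 0.05, by exact enumeration, is 0.328 overall and 0.157 per age group.

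**4. Rates taken from the protocol, as assumptions, at 740 against 148.**

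| Source | Vaccine / placebo | Fisher power |
|---|---|---|
| Phase 1, any systemic, Day 1 (2.1.6) | 26.7% / 23.3% | 12% |
| Flucelvax myalgia (Table 9) | 12% / 7% | 41% |
| Fluarix muscle aches (Table 13) | 23% / 12% | 88% |
| Flucelvax pain (Table 9) | 30% / 10% | about 100% |
| Phase 1, any local, Day 1 (2.1.6) | 66.7% / 26.7% | about 100% |

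**5. What the shells would omit.** Phase 1 systemic rates give 197/740 (26.6%) and 35/148 (23.6%), Fisher p = 0.48. The Wilson limits are 23.6 to 29.9% and 17.5 to 31.1%. The Newcombe interval for the +3.0-point difference is:
- lower: 3.0 - √((26.6 - 23.6)² + (31.1 - 23.6)²) = -5.1
- upper: 3.0 + √((29.9 - 26.6)² + (23.6 - 17.5)²) = +9.9

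(limits computed from unrounded values). By the same method:
- per age group, 99/370 against 17/74: +3.8 points (-7.8 to +13.2), p = 0.56
- a result just short of significance, 229/740 against 34/148: +8.0 points (-0.1 to +14.9), p = 0.061
- Phase 1 local rates, 493/740 against 39/148: +40.3 points (31.9 to 47.5), p about 10⁻¹⁹

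In the last case the test rejects overwhelmingly, and the informative result is the size of the excess.

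**6. Number of p-values.** Five CRF local items + 8 systemic + 2 any-event rows = 15; 15 × 2 windows × 3 age presentations = 90. With the protocol's three local items, 13 × 2 × 3 = 78. Table 14.3.1.1 adds any solicited, severe local and severe systemic: 3 × 2 × 3 = 18, so up to 108.

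**The case against.** The best defence is that the p-value has no official role. Protocol 13.7 describes safety by counts, proportions and exact CIs and disclaims formal testing. No passage makes p above 0.05 a criterion for safety. On this view the 17.1 pair is loose wording. That largely stands. It makes this a matter of wording and presentation, and it points to the same remedy, since a hypothesis that nothing tests should not be in the SAP.

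A second defence is that both arms' percentages and CIs sit beside each p-value, so the difference is one subtraction away and its CI can be computed from the printed counts. That is true. But two single-arm intervals are not an interval for the difference, and the reader is left to derive the quantity that matters.

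A reader might go further and infer one of these, none of which the documents support:
- That the solicited-event p-value is the sole between-arm safety result. The vital-signs shell has another: "P-value was computed using or 2-sample t test comparing vaccine groups". It too is a difference test without a CI.
- That the p-values stand with no effect size near them. The arm percentages are printed in every row.
- That the comparison is generally underpowered. Low power applies to modest, mainly systemic, excesses.
- That there is one exact number of p-values. It runs from 78 to 108, depending on how rows are counted.

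**Conclusion.** The point holds as a mismatch between a stated hypothesis and the planned analysis, together with a missing interval for the between-arm difference. The sizes rest on assumed true rates and full arms of 740 and 148. At 15% against 10%, power is 33% overall and 16% per age group. With Phase 1 systemic rates, a p-value of 0.48 is compatible with an excess of almost 10 points. Other interval methods move the limits by about a point or less for common events, and by up to about 2 points when the placebo count is zero.

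It would be too strong to say that the plan treats a non-significant test as proof of safety, because no such rule is written. Nor would a risk difference with a CI test the 17.1 alternative, since the documents give no margin; that is why 17.1 itself needs rewording. Sample size and the immunogenicity conclusions are unaffected.

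**What to change.** - **Shells.** In Table 14.3.1.1 and Tables 14.3.2.1.1 to 14.3.2.1.4, add a column for vaccine minus placebo, % (95% CI), by a score-type interval such as Miettinen-Nurminen or Newcombe, with the method named in the footnote. Limit it to solicited rows. The unsolicited, SAE and death rows of Table 14.3.1.1 stay as they are, since no testing is planned for them.
- **SAP 17.2.1.1 and 17.2.1.2.** State that the between-arm comparison is interpreted from the difference and its interval, and that the roughly 80 to 110 unadjusted p-values are descriptive.
- **SAP 17.1.** Replace the null and alternative with an estimation statement consistent with protocol 13.7. The general safety expectation in protocol 13.1 can then be cited as not formally tested.
- **SAP 3.3.** Record the added estimate, since that section now says nothing differs from the protocol.

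The cost is one column in five shells and a few SAP sentences, all from counts already tabulated.

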9. The participant will be given a Diary Card, thermometer and ruler in which the participant will be asked to record any local and/or systemic reactions that might appear starting from the evening of Day 1 to Day 7. Concomitant medications and other AEs may be recorded on the Dairy Card, too. The participant will be instructed how to use the Diary Card, thermometer and ruler. All relevant explanations should be included in the Diary Card. The Diary Card will also have contact information for the investigators, should the

participant have any questions. The participant will be informed that a member of the investigator's team will visit the participant the next 24 hours (Day 2) in phase 2 and visit/call in phase 3 and also call her/him 4 days (Day 5) after vaccination to check on the participant's completion of the Dairy Card and participant's well-being.

10. The participant will be instructed that if the participant experiences an AE requiring medical care, the participant should inform the investigator as soon as possible and seek medical care as appropriate. If the participant visits a health care provider, the participant should be sure to inform the health care provider of participation in this study and provide the health care provider with the investigator's contact information.

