### 10.3 AE/SAE Reporting Period and Parameter

Safety events are reported from the time of study injection (Day 1) through completion of the study at Day 91. Specifically, solicited AEs to assess local and systemic reactogenicities will be collected at 30 minutes and then daily for 7 days thereafter. If a solicited AE starts during the 7 days post vaccination period and continues beyond the 7 days it will continue to be reported as a solicited AE. SAEs will be reported from Day 1 through the end of the study at Day 91. Unsolicited AEs will be reported from Day 1 to Day 22 inclusive.

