**Study Object Descriptions: Contact**

Type	RefName	Description
Form	TELECONT	CONTACT

RDE Analytics: RD_TELECONT		
Data Variable RefName	RD Column Name	Column Data Type
TELEDATE	TELEDATE	DATE
	TELEDATE_DTS	VARCHAR2
	TELEDATE_ND	VARCHAR2
TELEYN	TELEYN_C	VARCHAR2
	TELEYN	VARCHAR2
	TELEYN_ND	VARCHAR2

IVACFLU-S-0203: SOLICITED LOCAL REACTOGENICITY (LOCAL) [SLR]	
Completed based on Memory Aids and Interview with Subject	
Local Reactogenicity [SLRSC]	
1.* ✓ Did the subject report any local reactogenicity during Days 1 to 7? [Did the subject report any local reactogenicity during Days 1 to 7?]	[SLRYN] [A:1]  Yes [A:2]  No
Pain at injection site [SLR2SC]	
2. ✓ Pain at injection site [Pain at injection site]	[SLRPAINWK] [A:1]  None all week
3. ✓ Evening Day 1 [Day 1 Pain at injection site]	[SLRPAIND1] [CIROGRES] ▾
4. ✓ Day 2 [Day 2 Pain at injection site]	[SLRPAIND2] [CIROGRES] ▾
5. ✓ Day 3 [Day 3 Pain at injection site]	[SLRPAIND3] [CIROGRES] ▾
6. ✓ Day 4 [Day 4 Pain at injection site]	[SLRPAIND4] [CIROGRES] ▾
7. ✓ Day 5 [Day 5 Pain at injection site]	[SLRPAIND5] [CIROGRES] ▾
8. ✓ Day 6 [Day 6 Pain at injection site]	[SLRPAIND6] [CIROGRES] ▾
9. ✓ Day 7 [Day 7 Pain at injection site]	[SLRPAIND7] [CIROGRES] ▾
10. ✓ After Day 7: Ongoing? [Ongoing]	[SLRPAINONG] [A:2]  No [A:1]  [SLRPAINONGCMP] Yes Highest severity until resolution: [SLRPAINSEV] [CISEV] ▾ [SLRPAINEDAT] End date Req ▾ / Req ▾ / Req ▾ (2017-2018)
Tenderness at injection site [SLR3SC]	
11. ✓ Tenderness at injection site [Tenderness at injection site]	[SLRTENDWK] [A:1]  None all week
12. ✓ Evening Day 1 [Day 1 Tenderness at injection site]	[SLRTENDD1] [CIROGRES] ▾
13. ✓ Day 2 [Day 2 Tenderness at injection site]	[SLRTENDD2] [CIROGRES] ▾
14. ✓ Day 3 [Day 3 Tenderness at injection site]	[SLRTENDD3] [CIROGRES] ▾
15. ✓ Day 4 [Day 4 Tenderness at injection site]	[SLRTENDD4] [CIROGRES] ▾
16. ✓ Day 5 [Day 5 Tenderness at injection site]	[SLRTENDD5] [CIROGRES] ▾
17. ✓ Day 6 [Day 6 Tenderness at injection site]	[SLRTENDD6] [CIROGRES] ▾
18. ✓ Day 7 [Day 7 Tenderness at injection site]	[SLRTENDD7] [CIROGRES] ▾
19. ✓ After Day 7: Ongoing? [Ongoing]	[SLRTENDONG] [A:2]  No [A:1]  [SLRTENDONGCMP] Yes Highest severity until resolution: [SLRTENDSEV] [CISEV] ▾ [SLRTENDEDAT] End date Req ▾ / Req ▾ / Req ▾ (2017-2018)

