Summary of Solicited Local Adverse Event Captured by Maximum Severity between Day 1 to Day 7  
Full Analysis Population

Source Data: Listing 16.2.7.3  
Programming Note: Repeat the template of Table 14.3.2.1.7

Table 14.3.2.2.2  
Summary of Solicited Systemic Adverse Event Captured by Maximum severity between Day 1 to Day 7  
Full Analysis Population

Source Data: Listing 16.2.7.3  
Programming Note: Repeat the template of Table 14.3.2.1.7 with corresponding Solicited Systemic events.

---

Document:	\\EEDC-NAS01A\Biosdata\Path\IVACFLU-S\IYA06804\Biostatistics \Documentation\SAP\IVACFLU-S-0203_Mock_Tables_V1.0	Version Number:	1.0
Author:	[name]	Version Date:	11AUG 2017]
Template No:	CS_TP_BS016 Revision 4	Reference:	CS_WI_BS005
Effective Date:	01Apr2016		

TABLE AND LISTING MOCK SHELL

Table 14.3.3.1.1  
Summary of Unsolicited Events  
Full Analysis Population

Age Group: <Overall> <18-45> <46-60>

Unsolicited event	Vaccine	Placebo	Total
	(N=xx) n (%) E	(N=xx) n (%) E	(N=xx) n (%) E
Total number of unsolicited AEs	xx	xx	xx
Subjects with at least one unsolicited AE	xx (xx.x) xx	xx (xx.x) xx	xx (xx.x) xx
At least one vaccine related unsolicited AE	xx (xx.x) xx	Xx (xx.x) xx	xx (xx.x) xx
At least one serious unsolicited AE	xx (xx.x) xx	xx (xx.x) xx	xx (xx.x) xx
At least one severe unsolicited AE	xx (xx.x) xx	xx (xx.x) xx	xx (xx.x) xx
At least one life threatening unsolicited AE	xx (xx.x) xx	xx (xx.x) xx	xx (xx.x) xx
Subjects requiring treatment during the study	xx (xx.x) xx	xx (xx.x) xx	xx (xx.x) xx
Subjects with unsolicited AEs leading to withdrawal	xx (xx.x) xx	xx (xx.x) xx	xx (xx.x) xx
Number of subjects died	xx (xx.x) xx	xx (xx.x) xx	xx (xx.x) xx

Data is based on the combined phases 2 and 3, pooled across study sites.

AE: Adverse Events

N= Total number of subjects in the relevant population per by-group stratification level, n= Number of subjects in each category, E= Number of Adverse Events, % = Calculated relative to the total number of subjects in the relevant population

AEs captured through day 22 were considered.

Any AE or solicited sign or symptom starting after 7 days post-vaccination will be recorded as an Unsolicited AE.

Source Data: Listing 16.2.7.4

Document: \\EEDC-NAS01A\Biosdata\Path\IVACFLU-S\IYA06804\Biostatistics \Documentation\SAP\IVACFLU-S-0203\_Mock\_Tables\_V1.0  
Author: [name]  
Version Number:  
Version Date:

1.0  
11AUG 2017]

Template No: CS\_TP\_BS016 Revision 4  
Effective Date: 01Apr2016

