...	...	...	...	

Programming Note: Sort by Treatment, Subject ID and Time point.

Document: \\IEEDC-NAS01A\Biosdata\Path\IVACFLU-S\IYA06804\Biostatistics \Documentation\SAP\IVACFLU-S-0203\_Mock\_Listings\_V1.0  
 Author: [name]  
 Version Number: 1.0  
 Version Date: [11AUG2017]

Template No: CS\_TP\_BS016 Revision 4  
 Effective Date: 01Apr2016  
 Reference: CS\_WI\_BS005

Copyright © 2009, 2010, 2012, 2016 Quintiles Transnational Corp. All rights reserved.  
 The contents of this document are confidential and proprietary to Quintiles Transnational Corp. Unauthorized use, disclosure or reproduction is strictly prohibited.

TABLE AND LISTING MOCK SHELL

Listing 16.2.7.3  
 Local and Systemic Solicited Reactogenicity by Maximum Severity between Day 1 to Day 7  
 Full Analysis Population

Treatment	Subject ID/ Site ID/ Age Group	Pain	Tenderness	Redness	Swelling	Hardness	Temperature (°C)	Fatigue/ Malaise	Muscle Aches	Joint Aches	Chills	Nausea	Vomiting	Headache
Vaccine	xxxxx/ xxxx/ xxxx	Mild	xxxx	xxx	xxxx	xxxx	Grade 0	Severe	xxx	xxx	xxx	xxx	xxxx	xxxx

Programming Note: Sort by Treatment and Subject ID.

Document: \\EEDC-NAS01A\Biosdata\Path\IVACFLU-S\IYA06804\Biostatistics \Documentation\SAP\IVACFLU-S-0203\_Mock\_Listings\_V1.0  
 Author: [name]  
 Version Number: 1.0  
 Version Date: [11AUG2017]

Template No: CS\_TP\_BS016 Revision 4  
 Effective Date: 01Apr2016  
 Reference: CS\_WI\_BS005

Copyright © 2009, 2010, 2012, 2016 Quintiles Transnational Corp. All rights reserved.  
 The contents of this document are confidential and proprietary to Quintiles Transnational Corp. Unauthorized use, disclosure or reproduction is strictly prohibited.

TABLE AND LISTING MOCK SHELL

Listing 16.2.7.4  
Unsolicited Adverse Events  
Full Analysis Population

Treatment	Subject ID/ Site ID/ Age Group	SOC/ Preferred Term/ Verbatim Term	Start Date/ End Date/ Study Day	Duration of AE (Days)	Severity/ Serious (Yes/No)	Relationship to Study Product	Action Taken/ Specification (e-CRF)	Outcome	Treatment Required (Yes/No)
Vaccine	xxxxx/ xxxx/ xxxx	Xxx/ xxxxx/ xxxx	DDMMYYYY/ DDMMYYYY/ xx	xx	Moderate/No	Not Related	None	Resolved	No

e-CRF: Electronic Case Report Form; MedDRA: Medical Dictionary for Regulatory Activities; SOC: System Organ Class  
Adverse Event terms were coded by SOC and Preferred Term using MedDRA version xx.x.  
Study day: Derived relative to administration date/time of vaccination.  

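### The SAP promises solicited-reaction severity as the maximum until resolution, but its severity tables and listing stop at Day 7, so a worse grade reached later would not be tabulated

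*Combined protocol and SAP*

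**What the plan says.** **Classification.** Protocol 10.3 says that when a solicited event starts in the 7 days after vaccination and goes on longer, "it will continue to be reported as a solicited AE". Protocol 10.1.1 and SAP 17.2.1 give the same rule. Under SAP 17.2.2, a solicited-type symptom becomes an unsolicited AE only if it starts after 7 days.

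**Data collected.** For each reaction, and for temperature, the eCRF solicited local and systemic forms ask whether it is ongoing after Day 7. If so, they record an end date and a grade under the label "Highest severity until resolution". The diary card sends such cases to a separate monitoring form for the period after Day 7.

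**SAP text.** SAP 17.2.1.2 says that "for all Solicited Local and Systemic Adverse Events the following will be summarised by maximum severity until resolution". It gives no Day 7 cut-off.

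**Shells.** Table 14.3.2.2.1 is titled "Summary of Solicited Local Adverse Event Captured by Maximum Severity between Day 1 to Day 7". Table 14.3.2.2.2 is "Summary of Solicited Systemic Adverse Event Captured by Maximum severity between Day 1 to Day 7". Both cite Listing 16.2.7.3, "Local and Systemic Solicited Reactogenicity by Maximum Severity between Day 1 to Day 7", which has one grade per reaction and no column for a later one. In Table 14.3.1.1 the follow-up rows for severe local and severe systemic events, with Fisher p-values, fall under a Day 1 to Day 7 heading. SAP section 8 makes the shells the description of what the final tables, listings and figures will contain.

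**The concern.** The text and the shells of one plan give two different severity variables for the same reactions, and the plan does not say which governs. A programmer who works from the shells would leave out a grade that the SAP text asks for and the site has recorded. The loss runs one way within an arm: ignoring later grades can lower a participant's maximum but cannot raise it.

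Solicited reactions are primary safety endpoints in a trial meant to support licensure, and the severe rows are the ones a reader looks at first. If the conflict is noticed only after unblinding, the choice between the two definitions becomes a post-hoc choice on those rows.

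**Working it through.** The plan states no figure on this point, so the check is mainly a comparison of texts.

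**1. Trace one reaction.** Take injection-site pain with onset on Day 3, mild through Day 7, severe on Day 9 and resolved on Day 11.

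| Place | How it is treated |
|---|---|
| Protocol 10.3, SAP 17.2.1 | Solicited throughout |
| eCRF local form | Day 3 to 7 grades mild; after-Day-7 highest severity Grade 3; end date Day 11 |
| SAP 17.2.1.2 text | Severe |
| Tables 14.3.2.2.1-2 and Listing 16.2.7.3, as titled | Mild |
| Table 14.3.1.1, follow-up severe row, as headed | Not counted |
| Unsolicited AE tables (14.3.3.1.x) | Not included, because onset was before the end of Day 7 |
| Incidence, Table 14.3.2.1.1, "Incidence of Solicited Local Adverse Events from Day 1 to Day 7" | Counted once, correctly |

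Unless the event is also serious and enters the SAE tables, its severe grade appears in no summary. The incidence row is right under either reading.

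**2. How often might it matter?** Inputs are from protocol 2.1.6 (phase 1), Table 15 and section 13.3.

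- Planned arms: vaccine 2 × 105 + 2 × 265 = 740; placebo 2 × 21 + 2 × 53 = 148.
- One reclassified participant moves a severe percentage by 100/740 = 0.14 points on vaccine, or 100/148 = 0.68 points on placebo.
- Phase 1 vaccinees: no local reaction beyond Day 4 and no systemic reaction beyond 6 days, so 0 of 30 would have reached the after-Day-7 field. The exact two-sided 95% upper limit is 1 − 0.025^(1/30) = 11.6%. That limit is 0.116 × 740, or about 86 vaccinees, for a reaction merely ongoing after Day 7. Only those who also worsened would change grade. The phase 1 data therefore point to few cases but are too small to rule them out.
- Severe solicited events in phase 1 vaccinees: 0 of 30 (protocol Table 3). A severe row that starts near zero is visibly changed by one or two events.

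**3. The start of the window.** Participants are asked to "record any local and/or systemic reactions that might appear starting from the evening of Day 1 to Day 7", while the 30-minute check has its own eCRF page. No text says whether a 30-minute finding counts as Day 1, and Listing 16.2.7.1 shows the two as separate time points. If a participants react at 30 minutes, b react in the Day 1 to 7 diary and c do both, the number with any reaction in the whole period is a + b − c. The shells give a and b but not c, so the total can only be placed between the larger of a and b, and a + b. Phase 1 had 0 of 60 reactions at 30 minutes (upper limit 1 − 0.025^(1/60) = 6.0%). If 1%, 2% or 5% of vaccinees (assumed values) reacted only at 30 minutes, about 7, 15 or 37 of 740 would be in the 30-minute tables and not in the Day 1 to 7 tables.

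**The case against.** The strongest reply is that this is a mismatch of titles. The shells contain no derivation rule excluding the after-Day-7 field, and the severity tables only say to repeat the layout of Table 14.3.2.1.7. Their titles could be read as naming the period in which the event was captured, with the grade followed to its end. The primary endpoint is also worded as Days 1 to 7, and keeping a continuing event classified as solicited does not by itself extend that period.

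Part of this stands. The alternative reading of the titles is possible, and a grade first reached after Day 7 lies outside the endpoint as literally worded. But the SAP text chose the wider severity window, and the eCRF was built to support it. The listing that feeds the tables carries the Day 7 limit without qualification. An ambiguity that yields two different severe counts needs one sentence to close it.

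A reader might also infer that immediate reactions drop out of the primary endpoint tables. The documents do not support that. The endpoint names 30 minutes and Days 1 to 7, and SAP 17.2.1.1 gives the first part its own analysis: incidence tables (14.3.2.1.3-4), severity tables (14.3.2.1.7-8), a size table (14.3.2.1.9) and a block in Table 14.3.1.1. Only a combined count and a Day 1 rule are missing.

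**Conclusion.** The conflict is real and should be corrected. As titled, Tables 14.3.2.2.1-2, Listing 16.2.7.3 and the follow-up severe rows of Table 14.3.1.1 do not deliver the maximum severity until resolution that SAP 17.2.1.2 specifies. A non-serious reaction that worsens after Day 7 would have its higher grade in the database and in no summary table.

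The size is probably small, on the assumption that this season's vaccine behaves like the phase 1 product. The conclusion also assumes that the shells are programmed as titled.

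Two further inferences would go too far. Solicited-event incidence is not understated by late worsening; only the grade is. Nor is there evidence that the mismatch favours the vaccine. Within an arm it can only lower the severe count, but the effect on the vaccine-placebo difference has no fixed direction. In phase 1 both severe reactions, and the reactions still being reported on Day 7, were in placebo recipients.

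**What to change.** Before unblinding:

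1. Retitle and derive Tables 14.3.2.2.1-2 and Listing 16.2.7.3 as onset Day 1 to Day 7, maximum severity until resolution. Take the worst of the Day 1 to 7 grades and the eCRF after-Day-7 highest severity, and state this in a footnote.
2. Apply the same rule to the follow-up severe rows of Table 14.3.1.1.
3. Keep the separate 30-minute tables unchanged.
4. Optionally, state in SAP 17.2.1.2 whether a 30-minute finding counts as Day 1. Also add one row for any time from vaccination through Day 7 to Tables 14.3.1.1 and 14.3.2.1.1-2, since the two existing rates cannot be added without double counting.

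The cost is shell and programming changes only, as every field is already collected. Severe percentages may rise slightly in either arm.
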